Appendix 1 Markedly Abnormal Laboratory Safety Values, Vital Signs and ECGs

Table A 1. Markedly abnormal Criteria for Laboratory Tests

Variable	Units	Markedly abnormal Criteria	
		Low	High
Haematology			
Haemoglobin	g/L	≤ 115	Not applicable
Haematocrit	Ratio	≤ 0.32	≥ 0.56
Total WBC	10 ⁹ /L	≤ 2.8	≥ 16.0
Eosinophils	%	Not applicable	≥ 10
Neutrophils	%	≤ 15	≥ 90
Lymphocytes	%	≤ 10	≥ 80
Monocytes	%	Not applicable	≥ 20
Basophils	%	Not applicable	≥ 5
Platelets	10 ⁹ /L	≤ 75	≥ 700
Total RBC	10 ¹² /L	≤ 3.5	Not applicable
Clinical Chemistry			
AST	IU/L	Not applicable	> 3xULN
ALT	IU/L	Not applicable	> 3xULN
Alkaline phosphatase	IU/L	Not applicable	> 3xULN and 25% increase from baseline
GGT	IU/L	Not applicable	> 3xULN
Total bilirubin	µmol/L	Not applicable	≥ 1.5xULN
Urea nitrogen	mmol/L	Not applicable	≥ 10.7
Creatinine	µmol/L	Not applicable	≥ 177
eGFR	mL/min	<30	Not applicable
Total protein	g/L	≤ 45	≥ 90
Albumin	g/L	≤ 25	≥ 65
Sodium	mmol/L	≤ 130	≥ 155
Potassium	mmol/L	≤ 3.0	≥ 5.8
Chloride	mmol/L	≤ 90	≥ 115
Calcium	mmol/L	≤ 1.8	≥ 3.9
Glucose	mmol/L	≤ 2.8	≥ 10
Coagulation			
INR		<0.8	>1.1
Activated partial thromboplastin time	Sec	Not applicable	>70

Table A 2. Markedly abnormal Criteria for Vital Signs*

Variable	Criterion Value	Change from Baseline
Systolic blood pressure	≥ 180 mmHg	Increase of ≥ 20 mmHg
	≤ 90 mmHg	Decrease of ≥ 20 mmHg
Diastolic blood pressure	≥ 105 mmHg	Increase of ≥ 15 mmHg
	≤ 50 mmHg	Decrease of ≥ 15 mmHg
Pulse rate	≥ 120 bpm	Increase of ≥ 15 bpm
	≤ 50 bpm	Decrease of ≥ 15 bpm
Body temperature		Increase to ≥ 39.4°C

* To be identified as markedly abnormal, a treatment value must meet the criterion value and also the specified change from baseline.

Table A 3. Abnormal Criteria for Quantitative ECG Data*

Variable	Abnormal Treatment-Emergent Value
ECG heart rate	≤ 50 bpm and decrease from baseline of ≥ 15 bpm ≥ 120 bpm and increase from baseline of ≥ 15 bpm
Duration of PR interval	> 220 msec
Duration of QRS interval	> 120 msec
Duration of QTc interval	> 450 msec
Duration of QTc interval	> 480 msec
Duration of QTc interval	> 500 msec
Duration of QTc interval	Increase from baseline of ≥ 30 msec
Duration of QTc interval	Increase from baseline of ≥ 60 msec

* QTc will be calculated using both Bazett's and Fridericia's corrections.

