## **1.3 Benefit / Risk Aspects**

The 95% granules allow for a true once a day convenient dosing with the highest unit dosage form available for induction and maintenance of UC. In addition the granules are easier to swallow than the tablets and capsules currently available in the US.

The most common adverse events (AEs) considered related to treatment with mesalamine formulations up to 4 g per day have been diarrhea, nausea, abdominal pain, headache, vomiting, and rash. Hypersensitivity reactions and drug fever may occasionally occur.

To mitigate risk, all subjects, including those in the placebo arm, will be offered early escape to local standard of care. Notably, all previous 5-ASA registration trials leading to an approval in the US utilized a placebo-controlled design.

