## **7.1.7 Clinical Laboratory Variables**

### **Hematology, Serum Chemistry, and Urinalysis**

Safety hematology, coagulation, and serum chemistry tests will be performed at Visit 0 (screening), Visits 4 and 5 (Week 8) or at early withdrawal during the double-blind treatment period, Visit 6 (Week 10) and Visits 7 and 8 (Week 16) during the open-label treatment period.

Hematology: hematocrit, hemoglobin, platelet count, red blood cell count, white blood cell count, and differential count

Coagulation: prothrombin time (measured as international normalized ratio), activated partial thromboplastin time

Serum chemistry: glucose, blood urea nitrogen, creatinine, creatinine clearance (via estimated glomerular filtration rate [eGFR]), potassium, sodium, chloride, calcium, total protein, albumin, total bilirubin, alkaline phosphatase, aspartate aminotransferase, alanine aminotransferase, and gamma glutamyl transferase

Urinalysis: leukocyte, blood, pH, specific gravity, nitrite, protein, glucose, urobilinogen, and microscopic if positive for blood, leucocytes, and nitrite

The investigator will review the laboratory results and evaluate and document whether the results are normal or abnormal and whether abnormal results are clinically significant. The laboratory report will be signed and dated by the investigator.

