10.3.3 Markedly Abnormal Changes

Number and percentage of subjects who experienced at least one pre-specified markedly abnormal value ([Appendix 1](#)) during the double-blind period for each laboratory variable will be summarized by the baseline category defined in Section 10.3.2 (i.e., low, normal, high, absent, or present).

For the open-label period, similar summaries will be provided for subjects who receive the open-label treatment.

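### SAP Table A 1 sets the neutrophil, lymphocyte and eosinophil limits only as percentages of white cells, so the markedly abnormal table can rank absolute counts in reverse; add absolute-count rows

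*SAP*

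**What the plan says.** Table A 1 in SAP Appendix 1 lists the white cell criteria. Total WBC is the only one in absolute units: low at or below 2.8, high at or above 16.0 x10^9/L. The differential is given in percent:

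- "Neutrophils % ≤ 15 ≥ 90"
- "Lymphocytes % ≤ 10 ≥ 80"
- "Eosinophils % Not applicable ≥ 10"
- "Monocytes % Not applicable ≥ 20"
- "Basophils % Not applicable ≥ 5"

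SAP 10.3.3 counts the subjects with "at least one pre-specified markedly abnormal value" in the double-blind period, one laboratory variable at a time and by baseline category. Nothing in the SAP combines WBC with the differential or converts a percentage to a count.

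Protocol 7.1.7 has both inputs measured ("white blood cell count, and differential count") without fixing the unit of the differential.

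The other planned laboratory outputs are summary statistics with minimum and maximum at Weeks 2 and 8 (SAP 10.3.1), Low/Normal/High shift tables from baseline to end of double-blind (10.3.2), and a listing of subjects with any abnormal value (10.3.4).

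**The concern.** A percentage limit depends on all the white cells as well as on the cell of interest. With WBC judged separately, a low count can sit just inside both limits, while a much higher count is flagged because other cells have increased. A table meant to show which arm had more marked hematology changes can then miss the lower count and report the higher one.

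This matters because abnormal laboratory values belong to the safety secondary endpoint, and Protocol 9.8.3 promises a count of subjects with potentially clinically significant values. Table A 1 appears to be how the SAP delivers that. The other outputs do not fill the same role. The shift table uses only the last double-blind observation, although hematology is also drawn at Week 2 and Visit 4, so a low value that recovers is absent from it. It also records direction, not degree. The listing gives no count by arm.

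**Working it through.** The documents state no absolute differential count, so there is no plan figure to reproduce. All limits below come from Table A 1.

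Formula: absolute count (x10^9/L) = WBC x percent / 100.

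**Step 1. The reversal, using the table's limits alone.**

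| Cell | WBC | Share | Absolute count | Limit for that cell |
|---|---|---|---|---|
| Neutrophils | 2.9 | 16% | 2.9 x 0.16 = 0.464 | not met |
| Neutrophils | 15.9 | 15% | 15.9 x 0.15 = 2.385 | met, low |
| Lymphocytes | 3.0 | 11% | 3.0 x 0.11 = 0.33 | not met |
| Lymphocytes | 15 | 10% | 15 x 0.10 = 1.5 | met, low |
| Eosinophils | 15.9 | 9.9% | 15.9 x 0.099 = 1.574 | not met |
| Eosinophils | 4.0 | 10% | 4.0 x 0.10 = 0.40 | met, high |

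For neutrophils, 2.385 / 0.464 = 5.1: the flagged low count is about five times the unflagged one.

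The first neutrophil case was also checked as a full differential: neutrophils 16, lymphocytes 70, monocytes 10, eosinophils 3 and basophils 1 (sum 100%) with WBC 2.9. None of the six white cell limits is met. For the second, 15/70/10/4/1 (same order, sum 100%) with WBC 15.9 meets only the low neutrophil limit.

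**Step 2. How low a neutrophil count can go unflagged.** To escape, WBC must exceed 2.8 and the share must exceed 15%, so the count must exceed 2.8 x 0.15 = 0.42. Every count at or below 0.42 therefore meets at least one of the two limits.

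**Step 3. Width of the gap under assumed cut-offs.** The documents give no absolute cut-off, so two are shown as assumptions.

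- Below 0.5: WBC must lie between 2.8 and 0.5 / 0.15 = 3.33, and the share between 15% and 0.5 / 2.8 = 17.9%.
- Below 1.0: WBC must lie between 2.8 and 1.0 / 0.15 = 6.67, and the share between 15% and 1.0 / 2.8 = 35.7%. For example, 20% of 4.0 = 0.80 meets neither limit.

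**Step 4. Flagged counts that may be unremarkable.** These rest on assumed reference limits.

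- Neutrophils at 15% reach an assumed lower limit of 1.5 to 2.0 once WBC is 10.0 to 13.3 (1.5 / 0.15; 2.0 / 0.15).
- Lymphocytes at 10% reach an assumed lower limit of 1.0 to 1.5 once WBC is 10 to 15.
- Eosinophils at 10% stay within an assumed upper limit of 0.35 to 0.5 while WBC is at most 3.5 to 5.0.

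**The case against.** The strongest reply is that this is a screening convention in one descriptive table, with no test attached, and that the data remain visible elsewhere. Much of that stands. The listing, the minimum and maximum, the shift tables and the investigator's review (Protocol 7.1.7, with clinically significant abnormalities reportable as adverse events under 7.1.6) all remain. No efficacy result depends on Table A 1. The reply does not restore a count by arm against marked limits over all visits, and if the other summaries are also in percent they share the blind spot.

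Four stronger readings are tempting, and the documents do not support them:

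- A reader might infer that severe neutropenia in general goes uncounted. It does not: counts at or below 0.42 are always flagged, so with an assumed cut-off of 0.5 the missed band is only about 0.42 to 0.50.
- A reader might infer that normal subjects are flagged. What counts as normal rests on reference limits the documents do not give. The flagged neutrophil example is also not an ordinary blood picture, since 70% lymphocytes of WBC 15.9 is 15.9 x 0.70 = 11.13.
- A reader might tie the gap to a known drug risk. Protocol 1.3 says "Hypersensitivity reactions and drug fever may occasionally occur", but it names neither neutropenia nor eosinophilia and does not link eosinophil counts to hypersensitivity.
- A reader might conclude that the percentage rows should be replaced. That would drop the high limits for neutrophils (90%) and lymphocytes (80%) unless new ones were written. It could also lose eosinophil flags: with an illustrative absolute limit of 1.5, 20% of WBC 7.0 = 1.4 would no longer count, nor would 10% at any WBC below 1.5 / 0.10 = 15.

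**Conclusion.** The point holds as a limited weakness in one safety tabulation. Percent-only limits applied variable by variable can flag a neutrophil count of 2.39 and pass one of 0.46 x10^9/L, with similar reversals for lymphocytes and eosinophils. That finding needs no outside figure. The width of the gap does: WBC 2.8 to 3.33 if 0.5 is assumed as the neutrophil cut-off, and 2.8 to 6.67 if 1.0 is assumed. The documents do not say how many subjects would fall there, and it is likely to be few. The gap is in the 10.3.3 summary, not in data capture, and the primary analysis is untouched. This is a cheap improvement.

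**What to change.** Keep every percentage row of Table A 1, including the high limits. Add absolute-count rows for neutrophils, lymphocytes and eosinophils, derived as WBC x percent / 100 from the same sample (or taken directly if the central laboratory already reports counts). The sponsor's medical lead should set the cut-offs before unblinding; none is proposed here. Tabulate the new rows under 10.3.3. Because that table is split by baseline category, state which reference range classifies the derived counts at baseline.

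The cost is one derived variable per cell type and a slightly longer table. Both inputs are already collected, so no new sample is needed.

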Appendix 2 Schedule of Trial Procedures

	Double-blind Treatment					Open-label Treatment (OL)			
	Screening	Baseline/ Randomization	Intermediate	Intermediate	End of Double-blind Treatment/ Early Withdrawal	OL Week 2	End of OL Treatment/ Early Withdrawal		
Visit	0	1	2	3	4	5	6	7	8
Week	Week -3	Week 0	Week 2	Week 4	Week 8		Week 10	Week 16	
Trial Day (visit window)	Up to Day -21	Day 1	Day 15 (±3 days)	Day 29 (±3 days)	Day 57 (-6 days)	Day 57 (±3 days)	Day 71 (±3 days)	Day 113 (-6 days)	Day 113 (±3 days)
Written informed consent	X								
Inclusion/exclusion criteria review	X	X							
Medical history	X	X							
Physical examination, including weight	X	X	X	X		X	X		X
Height	X								
Vital signs	X	X	X	X		X	X		X
12-lead electrocardiogram	X					X			X
Demographic data	X								
Serum/urine pregnancy test ^a	X	X				X			X
Drug and alcohol history	X								
Immunological testing for HBV, HCV, and HIV	X								
Estimated creatinine clearance	X ^b		X		X		X	X	
Safety hematology, coagulation, and chemistry	X ^b		X ⁱ		X ⁱ	X	X ⁱ	X ⁱ	X
Standard urinalysis ^c	X ^b		X			X	X		X
Stool sample	X ^b								
Randomization		X							
Prior and concomitant medications	X	X	X	X		X	X		X
Serum CRP		X	X	X		X	X		X
Fecal calprotectin stool sample		X				X			X
Clinical Response Score (stool frequency and rectal bleeding scores)	X		X	X	X		X	X	

	Double-blind Treatment					Open-label Treatment (OL)			
	Screening	Baseline/ Randomization	Intermediate	Intermediate	End of Double-blind Treatment/ Early Withdrawal		OL Week 2	End of OL Treatment/ Early Withdrawal	
Visit	0	1	2	3	4	5	6	7	8
Week	Week -3	Week 0	Week 2	Week 4	Week 8		Week 10	Week 16	
Trial Day (visit window)	Up to Day -21	Day 1	Day 15 (±3 days)	Day 29 (±3 days)	Day 57 (-6 days)	Day 57 (±3 days)	Day 71 (±3 days)	Day 113 (-6 days)	Day 113 (±3 days)
Flexible Sigmoidoscopy/ colonoscopy -Central reading	X ^d				X			X	
Calculation of Clinical and Endoscopic Response Score		X				X			X
Calculation of Modified Mayo score		X				X			
Physician's Global Assessment		X				X			
HRQoL questionnaire: IBDQ		X	X	X		X	X		X
Adverse event recording ^e	X	X	X	X		X	X		X
Distribution of trial medication		X	X	X		X ^f			X
First administration of trial medication ^g		X				X			
Trial medication collection/accountability			X	X		X			X
Trial medication compliance			X	X		X			X
Subject diary activation		X							
Subject diary data review ^h			X	X		X	X		X

Note: All subjects who discontinue treatment (double-blind or open-label) will complete end-of-treatment assessments.

- a For females of childbearing age or <1 year postmenopausal; if positive, the subject will not be enrolled in the trial. At screening, perform serum pregnancy test and at baseline and end of treatment (double-blind or open-label), perform urine pregnancy test. If the urine pregnancy test is positive at the end of double-blind treatment, the subject will not be enrolled in the open-label treatment period.
- b Results must be available at randomization, Visit 1.
- c If positive for blood, leucocytes, or nitrite microscopic urinalysis will be performed.
- d Baseline flexible sigmoidoscopy/colonoscopy will be scheduled during screening and must be completed after Clinical Response Score (Visit 0). It should be scheduled to occur no more than 10 days but at least 4 days prior to randomization (Visit 1) to allow sufficient time for the central reading. A colonoscopy will be required to establish the extent of disease if the flexible sigmoidoscopy is not conclusive in establishing the upper border of UC involvement.
- e Adverse events are collected from the signing of informed consent.
- f Open-label trial medication will be distributed for subjects entering the open-label treatment period only.
- g Double-blind trial medication first dose to be taken on Visit 1 Day 1; Open-label trial medication first dose to be taken the day following the end of double-blind treatment visit.
- h Subject daily diary data will be collected electronically and daily diary compliance will be assessed.

- i Only liver function tests and hematology.
- j No coagulation panel.
